7.2.3. Population of Interest

For frozen liquid cohort, CBR, TTR, and DoR will be analyzed using both ITT and Efficacy population, and other TTE endpoints will be analyzed using ITT population only.

For lyophilized cohort, all secondary efficacy endpoints will be analyzed using Lyo population.

7.2.4. Statistical Analyses / Methods

Details of the planned displays are provided in [Appendix 13](#): List of Data Displays and will be based on GSK data standards and statistical principles.

Unless otherwise specified, endpoints / variables defined in Section [7.2.1](#) will be summarised using descriptive statistics, graphically presented (where appropriate) and listed.

7.3. Exploratory Efficacy Analyses

7.3.1. Endpoint / Variables

7.3.1.1. Minimal Residual Disease (MRD) Negativity Rate

MRD negativity rate is defined as: the percentage of participants who are MRD negative by Next Generation Sequencing (NGS).

7.3.2. Summary Measure

7.3.2.1. MRD Negativity Rate

For MRD negativity rate based on bone marrow testing using Next Generation Sequencing (molecular negativity), the number and percentage of participants who have achieved MRD negativity will be summarized by dose level. The corresponding exact 95% CI for MRD negativity rate will also be provided. If data permit, duration of MRD negativity will be analysed using Kaplan-Meier method in participants who have achieved MRD negativity. Information of MRD will be included in the listing of response. If data is available, imaging-based assessment of MRD (i.e. PET-CT) will also be included in the listing and related to NGS testing.

7.3.3. Population of Interest

The exploratory efficacy analyses will be based on the ITT population for frozen liquid cohort, and Lyo population for lyophilized cohort.

7.3.4. Statistical Analyses / Methods

Details of the planned displays will be provided in [Appendix 13: List of Data Displays](#), based on GSK data standards, in the final version of the RAP.

8. SAFETY ANALYSES

The safety analyses will be based on the “Safety” population for frozen liquid cohort, and ‘Full Analysis’ population for frozen liquid cohort plus lyophilized cohort (side-by-side presentation). If needed, the safety analyses for lyophilized cohort alone will be based on the ‘Lyo’ population.

Unless otherwise specified, no ‘Total’ column will be provided for safety outputs, and the sorting will be based on descending order of incidence in 3.4 mg/kg arm. In case the 2.5 mg/kg becomes the selected dose post primary analysis, relevant outputs will be recreated with sorting based on descending order of incidence in 2.5 mg/kg arm

8.1. Adverse Events Analyses

Adverse events analyses including the analysis of adverse events (AEs), Serious AEs (SAEs) and other significant AEs will be based on GSK Core Data Standards.

An overview summary of AEs, including counts and percentages of subjects with any AE, AEs related to study treatment, Grade 3&4 AEs, Grade 3&4 AEs related to study treatment, AEs leading to permanent discontinuation of study treatment, AE leading to dose reductions, AEs leading to dose delays, AEs related to study treatment and leading to permanent discontinuation of study treatment, SAEs, SAEs related to study treatment, fatal SAEs, and fatal SAEs related to study treatment will be produced.

A summary of non-serious AEs that occurred in 5% of the subjects or above will be provided (no rounding for the percentage will be used in terms of 5% threshold, e.g., event with 4.9% incidence rate should not be included in this table). The summary will be displayed by SOC and PT.

The relationship between MedDRA SOC, PT, and Verbatim Text will be displayed.

Adverse events will be coded using the standard Medical Dictionary for Regulatory Affairs (MedDRA dictionary) and graded by the investigator according to the NCI-CTCAE, (version 4.03).

A summary of number and percentage of subjects with any adverse events by maximum grade will be produced. AEs will be sorted by Preferred term (PT) in descending order. The summary will use the following algorithms for counting the subject:

- **Preferred term row:** Subjects experiencing the same AE preferred term several times with different grades will only be counted once with the maximum grade.
- **Any event row:** Each subject with at least one adverse event will be counted only once at the maximum grade no matter how many events they have.

The frequency and percentage of AEs (all grades) will be summarized and displayed in two ways: 1) in descending order by PT only and 2) in descending order by SOC and PT. In the SOC row, the number of subjects with multiple events under the same SOC will be

counted once. In addition, a summary of cumulative incidence of AE by number of doses received at first occurrence will be provided.

A separate summary will be provided for study treatment-related AEs. A study treatment-related AE is defined as an AE for which the investigator classifies the relationship to study treatment as “Yes”. A worst-case scenario approach will be taken to handle missing relatedness data, i.e. the summary table will include events with the relationship to study treatment as ‘Yes’ or missing. The summary table will be displayed in two ways: 1) by maximum grade sorted by PT in descending order and 2) in descending order by SOC and PT.

In addition, AEs of maximum grade of 3 or higher will be summarized separately by PT.

All AEs will be listed. Additionally, a listing of subject IDs for each individual AE will be produced.

The details of the planned displays are provided in [Appendix 13: List of Data Displays](#).

8.2. Adverse Events of Special Interest Analyses

Adverse events of special interest for GSK2857916 include eye disorder, thrombocytopenia, infusion related reactions, and neutropenia graded via CTCAE, and corneal event per GSK scale.

8.2.1. Thrombocytopenia, infusion related reactions, and neutropenia

For thrombocytopenia and infusion-related reactions (IRR), in addition to events identified and collected in eCRF, a comprehensive list of MedDRA terms based on clinical review will be used to identify each type of event. For neutropenia, event will be identified using a comprehensive list of MedDRA terms based on clinical review. Changes to the MedDRA dictionary could occur between the start of the study and the time of reporting and/or emerging data from on-going studies may highlight additional adverse events of interest, therefore the list of terms to be used for each event of interest and the specific events of interest will be based on the SRT agreements in place at the time of reporting.

Summaries of the number and percentage of subjects with these events will be provided for each type of events separately by preferred term and maximum grade. The time to onset and duration of first occurrence for each type of events will be summarized using summary statistics mean, standard deviation, median, minimum value, and maximum. The number and percentage of subjects who have time to onset of first occurrence (1-21, 22-42, 43-63, >63 days) will be reported. The number and percentage of subjects who have duration of first occurrence (1-21, 22-42, >42 days) will be reported.

The summary of event characteristics will also be provided, including number of subjects with any event, number of events, number of subjects with any event that is serious, number of subjects with any event that is related to study treatment, number of occurrences (One, Two, Three or more), maximum grade, outcomes and the action taken for the event. The percentage will be calculated in two ways, one with number of subjects

with event as the denominator and the other with total number of subjects as the denominator. The worst-case approach will be applied at subject level for the maximum grade, i.e. a subject will only be counted once as the worst case from all the events experienced by the subject. For action taken to an event, subject will be counted once under each action, e.g. if a subject has an event leading to both study treatment discontinuation and dose reduction, the subject will be counted once under both actions. For each of these events, a summary of cumulative incidence by number of doses received at first occurrence will be provided.

For thrombocytopenia, number and percentage of subjects with grade 3 or 4 platelet count decreased (based on lab data) and concomitant grade 2 or above bleeding event will be summarized. A bleeding event will be considered as concomitant only if the start date is within ± 3 days of the lab event.

For neutropenia, number and percentage of subjects with grade 3 or 4 neutrophil count decreased (based on lab data) and concomitant infection event will be summarized. An infection event will be considered as concomitant only if the start date is within ± 7 days of the lab event.

The details of the planned displays are provided in [Appendix 13](#): List of Data Displays.

8.2.2. Eye disorder (CTCAE)

For AE in eye disorder SOC (CTCAE), an overview table and the listing will be provided.

In addition, for each of selected five types of event within eye disorder SOC (keratopathy, dry eye, blurred vision, photophobia, and eye pain), the following summary tables will be provided if the incidence rate $\geq 10\%$ is observed in 3.4mg/kg frozen liquid cohort

1. Event overview
2. Summary table by PT and Maximum Grade
3. Summary of event characteristics
4. Summary of time to onset, duration, and outcome
5. Summary of cumulative incidence by PT and number of doses received at first occurrence
6. Summary of percentage of time on study treatment with ongoing event

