2.3. Study Design

Overview of Study Design and Key Features	
	
 • Independent GSK2857916 Lyophilized Configuration Cohort 
 ○ Population: Subjects with relapsed/refractory MM (at least 25 subjects) ○ Objective: To assess the safety, efficacy, immunogenicity, and PK of GSK2857916 in a lyophilized configuration. • Ocular Sub-Study 
 ○ Population: Subjects with relapsed/refractory MM (up to 30 subjects (15 subjects each dose)) ○ Objective: evaluate the effect of topical corticosteroids on corneal findings in subjects who will receive monocular topical corticosteroids for the first 4 cycles and sign an optional ICF.
Dosing	
 • GSK2857916 Frozen Configuration Cohorts 
 ○ GSK2857916 will be administered at a calculated dose of 2.5 mg/kg or 3.4 mg/kg as an IV infusion over at least 30 minutes at the study sites. ○ Independent GSK2857916 Lyophilized Configuration Cohort 
 ○ GSK2857916 will be administered at a calculated dose of 3.4 mg/kg as an IV infusion over at least 30 minutes at the selected study sites when the lyophilized configuration becomes available. ○ Lyophilized configuration cohort will be initiated at 2.5 mg/kg if the results of the IA indicate that 3.4 mg/kg should not be continued. .
Time & Events	
 • Refer to Appendix 2: Schedule of Activities
Treatment Assignment	
 • This is a two-arm, randomized, multi-center, open-label study for GSK2857916 frozen configuration cohort. • For independent lyophilized cohort, there is only one dose group
Interim Analysis	
GSK2857916 Frozen Configuration Cohorts
 
 • One interim analysis (IA) is planned for the primary endpoint ORR after approximately 25 participants per arm are evaluable for response. Further details can be referred to in Section 3 of RAP and Section 4.1 of the protocol (Version: GSK Document Number TMF-13990464).

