3.1.1. Futility Stopping Rule Based on Group Sequential Design

For each arm (2.5 mg/kg or 3.4 mg/kg), a single futility IA is planned for the primary endpoint ORR after approximately 25 participants (~38% information fraction) per arm are evaluable. A user-defined gamma spending function ($\gamma=1.1$) [[Hwang, 1990](#)] was used as a beta-spending function to determine the non-binding futility boundary (as implemented in East 6.4). With this β -spending function, the stopping boundary in IA is identified as 0.16 on the proportion scale (4 responders out of 25 participants), which is close to the historical control of 0.15. The spending function and associated boundary were chosen to ensure good operating characteristics, specifically, the type 1 error and power are well controlled.

A two-step approach is used to identify the futility stopping rule based on a group sequential design under the assumption of exact binomial distribution.

First, as described in Section [3.1.1.1](#), an initial design based on the assumption of normal approximation of binomial proportion was identified by East 6.4.

The interim futility and primary efficacy analysis boundaries were then converted to number of responders needed in 25 participants per arm who are evaluable at IA and the 65 participants per arm initially planned at the primary analysis.

With a total sample size of 100 participants per arm and an IA with approximately 25 participants per arm, the same futility boundary (≤ 4 responders out of 25 participants) will still apply with a user-defined gamma spending function ($\gamma=5.4$). For the primary analysis, the boundary for claiming efficacy is the minimum number of responders required for the lower bound of the two-sided 97.5% exact C.I. to exceed 15% (i.e. 24 responders for sample size of 100 per arm).

Statistical properties of the group sequential design with sample sizes of 65, and 100 per arm are summarized in [Table 1](#).

Table 1 Probabilities of Crossing Boundaries at the Interim or Primary ORR Analysis based on Group Sequential Design

Look	Sample Size (per arm)	Boundaries	Cumulative Boundary Crossing Probabilities	
		# of Responders	Under H ₀	Under H ₁
Interim (futility)	25	≤4	68.21%	4.96%
Primary (Efficacy)	65	≥17	1.23%	88.00%
	100	≥24	0.97%	93.70%

Note: The Cumulative Boundary Crossing Probabilities are calculated based on exact binomial distribution theoretically.

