3.0580	Full Safety	AE3	Summary of Serious Adverse Events by Preferred Term		Headline, SAC [1], SAC [2]
3.0130	Full Safety	AE3	Summary of Adverse Events Leading to Permanent Discontinuation of Study Treatment by Preferred Term		IA [1], Headline, SAC [1] , SAC [2]
3.0140	Full Safety	AE3	Summary of All Serious Drug-Related Adverse Events by Preferred Term		SAC [1] , SAC [2]
3.0150	Full Safety	AE3	Summary of Adverse Events Leading to Dose Reduction by Preferred Term		Headline, SAC [1] , SAC [2]

CONFIDENTIAL

205678

Safety: Tables					
No.	Population	IDSL / Example Shell	Title	Programming Notes	Deliverable [Priority]
3.0160	Full Safety	AE3	Summary of Adverse Events Leading to Dose Delays by Preferred Term		Headline, SAC [1], SAC [2]
3.0830	Full Safety	AE6	Summary of Cumulative Incidence of Serious Adverse Events by PT and Number of Doses Received at First Occurrence	Only PT term, no SOC needed. The number of doses received at first occurrence will be <= 1, <= 2, <= 4, <= 6, <= 8, <= 10, and Any	SAC [1], SAC [2]
AEs of Special Interest					
3.0170	Full Safety	OAE07	Summary of Keratopathy Events (CTCAE) by Preferred Term and Maximum Grade	Table need to be created only if the observed incidence rate >= 10% in 3.4 mg/kg Frozen liquid cohort.	SAC [1], SAC [2]
3.0171	Evaluable	OAE07	Summary of Dry Eye Events (CTCAE) by Preferred Term and Maximum Grade (Evaluable)	Table need to be created only if the observed incidence rate >= 10% in 3.4 mg/kg Frozen liquid cohort.	SAC [1], SAC [2]
3.0172	Full Safety	OAE07	Summary of Blurred Vision Event (CTCAE) by Preferred Term and Maximum Grade	Table need to be created only if the observed incidence rate >= 10% in 3.4 mg/kg Frozen liquid cohort.	SAC [1], SAC [2]
3.0173	Full Safety	OAE07	Summary of Photophobia Event (CTCAE) by Preferred Term and Maximum Grade	Table need to be created only if the observed incidence rate >= 10% in 3.4 mg/kg Frozen liquid cohort.	SAC [1]
3.0174	Full Safety	OAE07	Summary of Eye Pain Event (CTCAE) by Preferred Term and Maximum Grade	Table need to be created only if the observed incidence rate >= 10% in 3.4 mg/kg Frozen liquid cohort.	SAC [1]
3.0180	Full Safety	ESI1	Summary of Characteristics of Keratopathy Events (CTCAE)	Table need to be created only if the observed incidence rate >= 10% in 3.4 mg/kg Frozen liquid cohort. Include summary of outcome of AE.	SAC [1], SAC [2]

CONFIDENTIAL

205678

Safety: Tables					
No.	Population	IDSL / Example Shell	Title	Programming Notes	Deliverable [Priority]

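### Event-specific eye tables depend on incidence in the 3.4 mg/kg frozen arm alone, so detail for 2.5 mg/kg can be withheld for events near the 10% cut-off

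*SAP*

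**What the plan says.** For the eye disorder class as a whole, SAP Section 8.2.2 is unconditional: "an overview table and the listing will be provided". For five named events (keratopathy, dry eye, blurred vision, photophobia, eye pain) it lists six further summaries, to be produced only if an incidence of 10% or more "is observed in 3.4mg/kg frozen liquid cohort".

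Appendix 13 (Section 15.13.8) repeats the condition table by table: "Table need to be created only if the observed incidence rate >= 10% in 3.4 mg/kg Frozen liquid cohort". The note stands against:

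- preferred term and maximum grade (3.0170-3.0174)
- characteristics (3.0180-3.0184)
- Characteristics II, whose shell covers onset, duration and outcome (3.0200-3.0204)
- event overviews (3.0251-3.0253, and the photophobia and eye pain overviews, both numbered 3.0250)
- percentage of duration of exposure with the event (3.1320-3.1324)

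It does not stand against the cumulative-incidence tables 3.0950-3.0954, although that summary is item 5 of the conditional list in Section 8.2.2.

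Section 8 sorts safety outputs by incidence at 3.4 mg/kg and provides for the other dose being chosen: "relevant outputs will be recreated with sorting based on descending order of incidence in 2.5 mg/kg arm". It says nothing about the 10% condition in that case.

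**The concern.** The tables display every treatment group, but only one group can cause them to be produced. Re-sorting for a selected dose of 2.5 mg/kg cannot restore a table that was never made. If an eye event reached 10% at 2.5 mg/kg and fell just short at 3.4 mg/kg, the plan would not require the onset, duration, outcome and time-with-event summaries for the dose carried forward.

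Section 8.2 lists eye disorder as an adverse event of special interest beside thrombocytopenia, infusion-related reactions and neutropenia. Section 8.2.1 gives those three comparable summaries with no incidence threshold. The SAP gives no reason for making the eye tables depend on one arm.

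**Working it through.** The SAP states no figure for this rule, so there is none to reproduce. The question is how often the condition would withhold the tables while the 2.5 mg/kg arm is at or above 10%.

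**Inputs.** Group sizes of 97 (2.5 mg/kg) and 96 (3.4 mg/kg) are the column totals in mock shell SAFE_T22. Section 3.1.1 plans for 100 per arm. The true event rates are assumptions, because the SAP gives none; a range of 10% to 30% is shown.

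**Cut-offs.** 9/97 = 9.3% and 10/97 = 10.3%, so 2.5 mg/kg reaches 10% with 10 or more participants. 9/96 = 9.4% and 10/96 = 10.4%, so the condition fails with 9 or fewer at 3.4 mg/kg.

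**Formula.** With independent arms, P(withheld and 2.5 mg/kg at or above 10%) = P(X ≥ 10; X ~ Bin(97, p2.5)) × P(Y ≤ 9; Y ~ Bin(96, p3.4)).

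| True rate 2.5 mg/kg | True rate 3.4 mg/kg | P(X ≥ 10) | P(Y ≤ 9) | Product |
|---|---|---|---|---|
| 10% | 10% | 0.509 | 0.505 | 25.7% |
| 12% | 12% | 0.741 | 0.271 | 20.1% |
| 15% | 15% | 0.931 | 0.075 | 7.0% |
| 20% | 20% | 0.997 | 0.004 | 0.4% |
| 30% | 30% | 1.000 | 0.000 | about 0 |
| 8% | 12% | 0.248 | 0.271 | 6.7% |
| 12% | 8% | 0.741 | 0.762 | 56.5% |

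With 100 per arm and the same method, the 10%/10% case is 24.8% and the 12% versus 8% case is 55.9%, so the result does not hang on the shell's column totals.

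**Lyophilized cohort.** With 25 participants, 2/25 = 8% and 3/25 = 12%, so three participants reach 10%. P(at least 3 of 25) is 12.7% at a true rate of 5% and 46.3% at 10%.

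**What is reported whatever the 3.4 mg/kg rate.** From Appendix 13:

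- all adverse events by preferred term and maximum grade (3.0040)
- cumulative incidence by number of doses at first occurrence, for all events (3.0560) and for the five eye events (3.0950-3.0954)
- events leading to discontinuation, dose reduction or delay (3.0130, 3.0150, 3.0160)
- the eye disorder overview (3.0250) and listing (1.0290)
- the corneal event tables on the GSK scale, including onset, duration and percentage of exposure
- at end of study, keratopathy Characteristics II (3.60100), and blurred vision and dry eye Characteristics II in participants with keratopathy (3.12791)

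Photophobia and eye pain are left with the least: for the full cohort, their characteristics, Characteristics II and percentage-of-exposure tables are all conditional, and all are marked for the primary analysis only (SAC [1]).

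**The case against.** The strongest defence is that this is a display rule for descriptive tables. It changes no inference, and using the higher dose as the reference is a conventional choice. The lyophilized cohort's default dose is also 3.4 mg/kg, so the trigger arm is the larger group at that dose. For an event well above 10% in that arm the rule never bites. All of that stands, and it keeps the point minor.

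A reader might infer that an eye signal at 2.5 mg/kg or in the lyophilized cohort would go unreported. The SAP does not support that: incidence, grade, action taken, doses to first occurrence and individual events appear for all groups regardless. Nor are all six summaries lost for each event, because Appendix 13 attaches no condition to cumulative incidence.

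A reader might also take the 57% case as the size of the problem. It assumes that the lower dose has the higher eye-event rate, for which the SAP gives no basis; with the rates reversed the figure is 6.7%. The largest values all come from rates close to the cut-off.

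Timing also limits the gain. This is RAP Amendment 2, dated 06 Apr 2022, and it describes primary-analysis pharmacokinetic work in the past tense. The conditional photophobia and eye pain tables are listed for the primary analysis only, so a new trigger alters nothing for them if that deliverable is closed. Most of the keratopathy, dry eye and blurred vision tables are also listed for end of study.

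What survives is the mismatch within Section 8: the plan provides for 2.5 mg/kg being selected and adjusts the sort order, but not the rule that decides whether the tables exist.

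**Conclusion.** The point holds as a low-severity improvement. As written, the plan can omit the event-specific overview, grade, characteristics, onset/duration/outcome and percentage-of-exposure tables for an eye event that reached 10% at 2.5 mg/kg. At equal true rates the chance per event is about 26% at the cut-off, 7% at 15%, and negligible from 20% upward. These figures rest on assumed rates, independent arms and 97 and 96 participants. The loss is of detail on special-interest events that are not common, and photophobia and eye pain have the least other coverage. Separately, item 5 of Section 8.2.2 and Tables 3.0950-3.0954 disagree on whether cumulative incidence is conditional.

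**What to change.** In Section 8.2.2, change the trigger to an incidence of at least 10% in either frozen liquid arm (2.5 or 3.4 mg/kg). Make the same change in the programming notes of Tables 3.0170-3.0174, 3.0180-3.0184, 3.0200-3.0204, 3.0251-3.0253, the photophobia and eye pain overviews, and 3.1320-3.1324. Apply it to every deliverable in which these tables are still to be run.

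The lyophilized cohort may be added as a further trigger, accepting that 3 of 25 participants would set it off: 13% of the time at a true rate of 5%, and 46% at 10%.

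State in both places whether cumulative incidence is conditional, so that item 5 of Section 8.2.2 and Tables 3.0950-3.0954 agree.

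The cost is a few extra tables from programs and shells that already exist. No hypothesis test or error rate changes.
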